5.3.2. PK Parameters

Actual PK sampling times will be used in the derivation of PK parameters. If a PK parameter cannot be derived from a participant’s concentration data, the parameter will be coded as NC (i.e., not calculated). (Note that NC values will not be generated beyond the day that a participant discontinues). In summary tables, statistics will be calculated by setting NC values to missing; and statistics will be presented for a particular treatment with ≥ 3 evaluable measurements. PK parameter analyses will not be performed for a particular parameter if more than 50% of the data are NC.

If an individual participant has a known biased estimate of a PK parameter (due for example to an unexpected event such as vomiting before all the compound is adequately absorbed from the gastrointestinal tract), this will be footnoted in summary tables and will not be included in the calculation of summary statistics or statistical analyses.

6. ANALYSES AND SUMMARIES

6.1. Primary Endpoints

The primary endpoints C_{max} and AUC_{inf} (if data permits, otherwise AUC_{last}) will be summarized descriptively by treatment and will include the set of summary statistics as specified in [Table 4](#). Box and whisker plots for individual participant parameters (C_{max} , AUC_{inf} and AUC_{last}) will be plotted by treatment and overlaid with geometric means.

Natural log transformed parameters C_{max} and AUC_{inf} (if data permits, otherwise AUC_{last}) of PF-07817883 will be analyzed using a mixed effect model with treatment as fixed effect and participant as a random effect. Estimates of the adjusted means, adjusted mean differences (Test-Reference) and corresponding 90% CIs will be obtained from the model. The adjusted mean differences and 90% CIs for the differences will be exponentiated to provide estimates of the ratio of adjusted geometric means (Test/Reference) and 90% CI for the ratios. PF-07817883 administered alone will be the Reference treatment and PF-07817883 co-administered with itraconazole will be the Test treatment.

For C_{max} , AUC_{inf} and AUC_{last} , a listing of the individual participant ratios (Test/Reference) will be provided.

Residuals from the model will be examined for normality and the presence of outliers via visual inspection of plots of residuals vs predicted values and normal probability plots of residuals but these will not be included in the CSR. If there are major deviations from normality or outliers then the effect of these on the conclusions will be investigated through alternative transformations and/or analyses excluding outliers. Justification for any alternative to the planned analysis will be provided in the clinical study report.

6.2. Secondary Endpoints

6.2.1. Safety data

Safety data will be analyzed in accordance with the CaPS (described in [Section 6.5](#)).

6.2.2. Other PK parameters

T_{max} , $t_{1/2}$, CL/F and V_z/F will be summarized descriptively by treatment and will include the set of summary statistics as specified in [Table 4](#).

PK parameter summaries:

The PF-07817883 PK parameters will be summarized descriptively by treatment in accordance with Pfizer data standards for the PK Parameter Set, as data permit. Missing values will be handled as detailed in [Section 5.3.2](#). Each PF-07817883 PK parameter will be summarized by treatment and will include the set of summary statistics as specified in [Table 4](#).

Table 4. PK Parameters to be Summarized Descriptively by Treatment

Parameter	Summary Statistics
AUC _{inf} , AUC _{last} , AUC ₁₂ , AUC ₂₄ , C _{max} , CL/F, V _z /F, Ae ₂₄ , Ae _{24%} , CL _R	N, arithmetic mean, median, SD, %CV, minimum, maximum, geometric mean and geometric %CV
T _{max}	N, median, minimum, maximum
t _{1/2}	N, arithmetic mean, median, SD, %CV, minimum, maximum

N: Number of participants contributing to the summary statistics

Supporting data from the estimation of t_{1/2} and AUC_{inf} will be listed by treatment: terminal phase rate constant (k_{el}); goodness of fit statistic from the log-linear regression (r²); the percent of AUC_{inf} based on extrapolation (AUC_{extrap} %); and the first, last, and number of time points used in the estimation of k_{el}. This data may be included in the clinical study report.

PK concentration summaries:

The plasma concentrations of PF-07817883 will be listed and descriptively summarized by nominal PK sampling time and treatment for the PK Concentration Set. Individual participant and summary profiles (mean and median plots) of the plasma concentration-time data will be plotted by treatment using actual and nominal times, respectively. Mean and median PF-07817883 plasma concentration profiles will be presented on both linear and semi-log scales.

Presentations for PF-07817883 plasma concentrations will include:

- A listing of all concentrations sorted by participant ID, treatment and nominal time postdose. The concentration listing will also include the actual times. Deviations from the nominal time will be provided in a separate listing.
- A summary of concentrations by treatment and nominal time postdose, where the set of statistics will include n, mean, median, SD, %CV, minimum, maximum and the number of concentrations above the LLQ.
- Median concentrations time plots (on both linear and semi-log scales) against nominal time postdose by treatment (all treatments on the same plot per scale, based on the summary of concentrations by treatment and time postdose).
- Mean concentrations time plots (on both linear and semi-log scales) against nominal time postdose by treatment (all treatments on the same plot per scale, based on the summary of concentrations by treatment and time postdose).
- Individual concentration time plots by treatment (on both linear and semi-log scales) against actual time postdose (there will be separate spaghetti plots for each treatment per scale).

- Individual concentration time plots by participant (on both linear and semi-log scales) against actual time postdose [there will be separate plots for each participant (containing all treatments) per scale].

6.2.3. Other Endpoints – Exploratory PK Endpoints

AUC₁₂ and C_{max} derived from blood samples collected using the Tasso® M20 device adjusted for B/P ratio will be summarized for PF-07817883 (administered alone in Period 1) and will include the set of summary statistics as specified in [Table 4](#). Summary statistics of the whole blood concentrations, plasma equivalent concentrations by microsampling using individual B/P ratio and plasma equivalent concentrations by microsampling using geometric mean B/P ratio at nominal time of collection as defined in SoA will be calculated.

Furthermore, to determine correlation in concentrations derived from time matched Tasso® M20 microsampling (calculated using individual or population) and traditional venous plasma sampling, Bland-Altman plot analysis will be performed to evaluate the bias and SD of the bias between the mean differences and to estimate an agreement interval within a 95% confidence limit. A concentration correlation analysis will be conducted with the same dataset.

In addition, Ae₂₄, Ae_{24%} and CL_R, derived from PF-07817883 concentrations measured from urine samples collected (if analyzed) will be summarized by treatment and will include the set of summary statistics as specified in [Table 4](#).

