## 4.2. Scientific Rationale for Study Design

As PF-07817883 is primarily metabolized by CYP3A, a strong inhibitor of that enzyme (eg, itraconazole) is expected to increase the systemic exposure of PF-07817883. Itraconazole and its primary metabolite (hydroxy-itraconazole) are specific strong inhibitors of CYP3A. For these characteristics, along with its safety profile, itraconazole has often been utilized as a perpetrator drug for CYP3A inhibition PK drug interaction studies. Given the metabolism profile of PF-07817883, concomitant administration of multiple doses of itraconazole along with PF-07817883 may lead to increased systemic exposure of PF-07817883. In the proposed study, in Period 2, itraconazole will be administered as a solution (200 mg QD) for 3 days prior to coadministration with PF-07817883 (Period 2 Day 4). Although 3 days is insufficient for attainment of steady state of itraconazole (effective half-life of 24 h), the 3-day lead-in allows for some accumulation, with higher itraconazole and the metabolite exposure and therefore a potentially greater degree of CYP3A inhibition. Dosing itraconazole for longer than 3 days prior to coadministration with a CYP3A substrate did not appear to provide additional inhibitory effect. CCI [REDACTED]

With CYP3A inhibition, the half-life of PF-07817883 is anticipated to increase. In order to sufficiently capture the elimination phase, in both periods of the proposed study, PK sampling will continue until 96 hours post PF-07817883 dose. PK microsampling will be explored in Period 1 to examine concordance between concentrations of PF-07817883 measured in the traditional PK samples versus the microsamples. Multiple microsamples collected following the PF-07817883 dose in Period 1 would allow for AUC calculations. If the concordance is found to be acceptable, in future studies, microsampling has a potential to decrease study burden on patients. Estimate of the blood/plasma ratio is essential as it is used as a scaling factor to estimate the concordance between the concentration of PF-07817883 measured through 2 sampling methods.

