2.2. Study Objectives, Endpoints, and Estimands

The following are the objectives and endpoints in this study. Estimand framework will not be applied to this Phase 1 study in healthy participants.

Objectives	Endpoints
Primary:	Primary:

 • To estimate the effect of multiple doses of itraconazole 200 mg QD on the PK of PF-07817883 following a single oral dose of PF-07817883 300 mg 	
 • PF-07817883 plasma PK parameters: C_{max} and AUC_{inf} (if data permits, otherwise AUC_{last}) with itraconazole (test) versus without itraconazole (reference)
Secondary:	Secondary:

 • To evaluate the safety and tolerability of PF-07817883 in healthy participants in the absence and presence of multiple doses of itraconazole • To characterize additional PK parameters of PF-07817883 when administered alone or with itraconazole in healthy participants 	
 • Assessment of TEAEs, clinical laboratory abnormalities, vital signs, physical exams, and 12-lead ECGs • PF-07817883 plasma PK parameters: T_{max}, and if data permits, $t_{1/2}$, CL/F, V_z/F, with and without coadministration of itraconazole
Tertiary/Exploratory:	Tertiary/Exploratory:

 • To assess the similarity of PK in blood by microsampling technique(s) with those in plasma by venipuncture • To characterize additional PK parameters of PF-07817883 following a single oral dose of PF-07817883 with and without itraconazole by renal function • To evaluate the drug-product acceptability of PF-07817883 	
 • Concentration of PF-07817883 in blood and plasma as well as PF-07817883 plasma PK parameters: AUC_{12}, C_{max} • Concentration of PF-07817883 in urine and urine PF-07817883 PK parameters: Ae_{24}, CL_R, if applicable and as data permits • Score on a 14-item drug-product acceptability questionnaire

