3.3. Other Endpoints

3.3.1. Exploratory PK Endpoints

Blood (by microsampling using the Tasso® M20 device) and urine samples for urine PK analysis of PF-07817883 will be taken according to the SoA given in the protocol. For each individual, a blood to plasma (B/P) ratio will be calculated by dividing concurrent (i.e. Day 1, 1 hour post-dose) whole blood PF-07817883 concentration with the plasma PF-07817883 concentration. A geometric mean and CV% of the B/P ratio from all individuals will also be calculated. The plasma equivalent PF-07817883 concentration by microsampling will be calculated by dividing with the individual B/P ratio. As a sensitivity analysis, the plasma

equivalent concentration will also be calculated using the geometric mean B/P ratio from all individuals. AUC₁₂ and C_{max} will be derived from blood samples collected using the Tasso® M20 device, and then adjusted for B/P ratio. Concentration of PF-07817883 in urine will be analyzed and additional urine PK parameters defined in Table 3 will be derived.

Table 3. Urine PF-07817883 PK parameter definitions

Parameter	Definition	Method of Determination
Ae_{24}	Total amount of unchanged drug excreted in the urine over 24 hours	Sum of amount excreted for each collection period.
$Ae_{24\%}$	Total amount of unchanged drug excreted in the urine over 24 hours, expressed as percent of dose	$100 \times (Ae_{24}/Dose)$
CL_R	Renal clearance	Ae_{24}/AUC_{24}

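### Device and venous AUC12 and Cmax are summarised separately, with no paired ratio or interval, and apparently on different sampling times

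*SAP*

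**What the plan says.** One exploratory objective (Protocol Section 3, SAP 2.2) reads "To assess the similarity of PK in blood by microsampling technique(s) with those in plasma by venipuncture". Its endpoints are "Concentration of PF-07817883 in blood and plasma as well as PF-07817883 plasma PK parameters", the parameters being AUC12 and Cmax. Protocol 4.2 gives a reason for taking several microsamples: "Multiple microsamples collected following the PF-07817883 dose in Period 1 would allow for AUC calculations".

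SAP 3.3.1 states that AUC12 and Cmax "will be derived from blood samples collected using the Tasso® M20 device, and then adjusted for B/P ratio". SAP 6.2.3 then handles the two kinds of endpoint differently:

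- **Parameters.** For device AUC12 and Cmax the plan is descriptive: "M20 device adjusted for B/P ratio will be summarized for PF-07817883 (administered alone in Period 1", using the Table 4 statistics.
- **Concentrations.** The comparison with venous plasma is introduced as being "to determine correlation in concentrations derived from time matched Tasso® M20 microsampling". It has two parts: "Bland-Altman plot analysis will be performed to evaluate the bias and SD of the bias between the mean differences", together with an agreement interval; and "A concentration correlation analysis will be conducted with the same dataset".

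Venous AUC12 and Cmax are summarised by treatment under SAP 6.2.2 and Table 4. The mixed model and the listing of individual ratios (SAP 6.1) and the code in SAP Appendix 2 concern itraconazole versus no itraconazole. SAP Appendix 1 has no row for device versus venous parameters.

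**The concern.** Two of the endpoints named for a similarity objective have no planned analysis of similarity. The device and venous values come from the same participants after the same dose, so the natural quantity is each participant's device/venous ratio. Two separate summaries report neither how much that ratio varies between participants nor how precisely its mean is known.

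The concentration analysis does not supply this. Bland-Altman limits describe single samples. In an AUC, independent sample errors partly average out, while a participant's B/P ratio scales every point alike. Cmax is a maximum over the sampled times and has its own error.

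There is also a question of schedule. If the device is sampled at fewer times than the vein, a difference between the two AUC12 or Cmax summaries could come from the sampling times and not from the device. At stake is how well the study informs later use of microsampling for exposure parameters, not any conclusion about itraconazole.

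**Working it through.** The documents give no figure for device-venous agreement of parameters, so there is none to reproduce.

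**1. What the two planned summaries already give.** Write D for a participant's device value (plasma equivalent) and V for the venous value. If the same n participants enter both summaries, GM(D)/GM(V) = exp(mean ln D − mean ln V) = exp(mean of ln(D/V)). The crude ratio therefore equals the paired point estimate, for whatever sampling times each parameter was computed on.

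**2. What they do not give.** The interval needs the SD of ln(D/V). With equal log-SD s for both methods and correlation ρ, that SD is s√(2(1−ρ)), and ρ is not reported. Illustration with n = 10 (the evaluable number in Protocol 9.5), an assumed geometric CV of 30% for each method (s = √ln(1.09) = 0.294), a ratio of 1.00 and t(0.95; 9) = 1.833:

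| ρ | SD of ln(D/V) | 90% CI |
|---|---|---|
| 0 | 0.415 | 0.786 to 1.272 |
| 0.5 | 0.294 | 0.844 to 1.186 |
| 0.9 | 0.131 | 0.927 to 1.079 |

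Identical summaries are compatible with all three rows. High correlation is to be expected after a shared dose, but the reader could not tell how high.

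**3. What a paired analysis would give.** The 90% half-width on the log scale is t(0.95; n−1) × SD/√n. The SD is not in the documents, so 0.10 to 0.20 is assumed.

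- n = 10, SD 0.10: 1.833 × 0.10/√10 = 0.058, or ×/÷ 1.06
- n = 10, SD 0.15: 0.087, or ×/÷ 1.09
- n = 10, SD 0.20: 0.116, or ×/÷ 1.12
- n = 12 (all enrolled), SD 0.10 to 0.20: ×/÷ 1.05 to 1.11

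**4. Sampling times.** As extracted, Protocol Table 2 marks the device at 0.5, 1, 2 and 6 h. Its venous schedule up to 12 h lists 0, 0.5, 1, 1.5, 2, 4, 6, 8 and 12 h. The blood/plasma mark falls at 1 h, which agrees with SAP 3.3.1. However, the table was machine-read, so the columns must be confirmed in the original.

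If they are right, the crude ratio splits into two factors:

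D/V(all times) = [D/V(device times)] × [V(device times)/V(all times)]

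The first factor is the method and the second is the schedule. For Cmax the second factor cannot exceed 1, because a maximum over a subset of times cannot exceed the maximum over all of them. So even a perfect device could appear to read low. For AUC12 the direction is not fixed: the device curve would have to be extended from 6 to 12 h, and the SAP gives no rule for that.

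**5. The two B/P versions.** With b the individual B/P ratio, and the same participants throughout, dividing by each b or by GM(b) gives the same geometric mean device value, GM(blood value)/GM(b). The two versions can differ only in spread, which is what an interval and individual ratios would show.

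**The case against.** The strongest reply is that the SAP already analyses what the protocol asks. Protocol 4.2 frames the microsampling question as concordance of concentrations, and its remark about future studies refers to that concordance. SAP 6.2.3 plans this comparison on time-matched samples with bias, SD and an agreement interval, which avoids the schedule problem. A systematic B/P error would shift concentrations proportionally and appear in the Bland-Altman bias, and a geometric-mean B/P version is planned as sensitivity. The objective is exploratory, no hypothesis is tested, and the endpoint text does not demand a ratio.

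Most of this stands, and it rules out several stronger readings that a reader might infer:

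- *Similarity of parameters gets no estimate.* Step 1 shows that a crude ratio can be read from the summaries.
- *Future use of microsampling hangs on AUC12 and Cmax.* Protocol 4.2 ties it to concentrations.
- *Separate summaries leave the ratio uncertain to ×/÷ 1.15 to 1.32.* That range (n = 12, between-participant log-SD 0.2 to 0.4) comes from treating the device and venous values as two independent groups. They are paired, so it is not the uncertainty of the ratio.
- *A B/P bias would go unseen.* The planned Bland-Altman analysis would show it.

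A fair further objection is that an unmatched ratio with a confidence interval could make a sound device look dissimilar. That is an argument for matching the times. The planned side-by-side summaries have the same fault.

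**Conclusion.** The point holds in a limited form. AUC12 and Cmax are named endpoints of the similarity objective, yet the plan compares the two methods on concentrations only. For the parameters, a crude ratio is available, but no paired interval and no spread of individual ratios is planned. The crude ratio also appears to mix method with sampling schedule, subject to confirming the columns of Protocol Table 2.

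Under an assumed log-ratio SD of 0.10 to 0.20 and 10 participants, a paired 90% interval of about ×/÷ 1.06 to 1.12 would be obtainable from data already collected. This is a worthwhile improvement to an exploratory output, not a defect in the study's main purpose. The primary analysis is unaffected.

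**What to change.** Confirm the device sampling times, then add to SAP 6.2.3, with a matching row in Appendix 1:

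> For Period 1, AUC and Cmax from the device (plasma equivalent) and from venous plasma will be compared within participant on the log scale. The device/venous geometric mean ratio with 90% CI and a listing of individual ratios will be reported. Venous values for this comparison will be recomputed on the nominal times of the device samples, with time zero handled alike for both methods. If there is no 12 h device sample, AUC will be truncated at the last common time. The individual B/P ratio will be used, with the geometric-mean B/P ratio as sensitivity.

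The Appendix 2 model can be reused with sampling method in place of treatment. The concentration-level Bland-Altman and correlation analyses stay as planned.

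The cost is one extra table, one listing and a second, time-matched venous derivation. No new samples are needed. If the AUC is truncated, the comparison describes a shorter window than AUC12, and the report should say so.

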6.2.4. Drug-Product Acceptability

For each item in the Drug-Product Acceptability Questionnaire, summary statistics will include number and percent with each numeric score (1,2,3,4,5) and negative (1, 2), neutral (3) and positive (4, 5) scores and will be presented by item and domain (Appearance, Mouthfeel, Taste, Swallowability and Overall assessment).

6.3. Subset Analyses

There are no planned subset analyses.

6.4. Baseline and Other Summaries and Analyses

6.4.1. Demographic Summaries

Demographic characteristics will be summarized for enrolled population in accordance with the CaPS.

6.4.2. Study Conduct and Participant Disposition

Participants evaluation groups will show end of study participant disposition. Frequency counts will be supplied for participant discontinuation(s) by treatment. Data will be reported in accordance with the CaPS.

6.4.3. Study Treatment Exposure

Study treatment exposure will be listed.

6.4.4. Concomitant Medications and Nondrug Treatments

All concomitant medication(s) as well as non-drug treatment(s) will be reported in the listings.

6.5. Safety Summaries and Analyses

All safety analyses will be performed on the Safety Analysis Set.

Safety data will be presented in tabular and/or graphical format and summarized descriptively, where appropriate.

Safety data will be summarized for three (3) separately defined treatments: (i) PF-07817883 300 mg SD (from Period 1 Day 1 up to just before the first dose of itraconazole administered alone in Period 2 Day 1), (ii) itraconazole 200 mg QD alone (from first dose of itraconazole administered alone in Period 2 Day 1 up to just before coadministration of PF-07817883 in Period 2 Day 4), and (iii) itraconazole 200 mg QD with PF-07817883 300 mg SD (from coadministration of PF-07817883 with itraconazole in Period 2 Day 4 through the end of the study).

A set of summary tables split by these 3 treatments will be produced to evaluate any potential risk associated with the safety and tolerability of administering PF-07817883 300 mg SD alone, itraconazole 200 mg QD alone, and PF-07817883 300 mg SD in the presence of itraconazole 200 mg QD.

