Participants will receive itraconazole 200 mg, administered orally QD on Period 2 Days 1 through 7 (Study Days 5-11), inclusive. On Period 2 Day 1 the itraconazole dosing will take place approximately 1 hour following the last PK sample collection on that day (96 hours post-dose time point). On Period 2 Day 4 (Study Day 8), participants will receive PF-07817883 300 mg administered orally immediately after the itraconazole dose for that day, after which the participants will undergo serial PK sampling up to 96 hours and urine will be collected up to 24 hours following the PF-07817883 dose on Period 2 Day 4. As a result, the washout interval between dosing of PF-07817883 in Period 1 and Period 2 is 7 days. Participants may be confined at the PCRU during the entire duration of the study, and they will be discharged from the PCRU on Period 2 Day 8 (Study Day 12) following completion of all assessments.

The participants will be fasted overnight for at least 10 hours before administration of PF-07817883 (Period 1 Day 1 [Study Day 1] and Period 2 Day 4 [Study Day 8]). Details of meal and water restrictions along with other necessities are elaborated in Section 5.3 Lifestyle Considerations.

If a participant has any clinically significant, study-related abnormalities at the conclusion of a scheduled inpatient portion of the study, the Pfizer medical monitor (or designated representative) should be notified and the participant may be asked to remain in the PCRU until such abnormalities are deemed not clinically significant, or it is safe for outpatient follow-up.

A follow-up (which may be a phone call) will be made to participants approximately 28 to 35 days from administration of the final dose of study intervention.

The total planned duration of participation, from the Screening visit to the last follow-up, is approximately 13 weeks.

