### **6. STUDY INTERVENTION(S) AND CONCOMITANT THERAPY**

Study interventions are all prespecified investigational and noninvestigational medicinal products, medical devices, and other interventions (eg, surgical and behavioral) intended to be administered to the study participants during the study conduct.

For the purposes of this protocol, study intervention refers to PF-07817883 or itraconazole.

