#### **8.4.1. Time Period and Frequency for Collecting AE and SAE Information**

The time period for actively eliciting and collecting AEs and SAEs (“active collection period”) for each participant begins from the time the participant provides informed consent, which is obtained before undergoing any study-related procedure and/or receiving study intervention), through and including a minimum of 28 calendar days, except as indicated below, after the last administration of the study intervention.

Follow-up by the investigator continues throughout the active collection period and until the AE or SAE or its sequelae resolve or stabilize at a level acceptable to the investigator.

When a clinically important AE remains ongoing at the end of the active collection period, follow-up by the investigator continues until the AE or SAE or its sequelae resolve or stabilize at a level acceptable to the investigator and Pfizer concurs with that assessment.

For participants who are screen failures, the active collection period ends when screen failure status is determined.

If the participant withdraws from the study and also withdraws consent for the collection of future information, the active collection period ends when consent is withdrawn.

If a participant permanently discontinues or temporarily discontinues study intervention because of an AE or SAE, the AE or SAE must be recorded on the CRF and the SAE reported using the CT SAE Report Form.

Investigators are not obligated to actively seek information on AEs or SAEs after the participant has concluded study participation. However, if the investigator learns of any SAE, including a death, at any time after a participant has concluded study participation, and they consider the event to be reasonably related to the study intervention, the investigator must promptly report the SAE to Pfizer using the CT SAE Report Form.

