3.5.1. Adverse Events

Any adverse events occurring following start of treatment will be considered as treatment emergent adverse event (TEAE). Events that occur during follow-up within the lag time of up to 35 days after the last dose of study intervention will be counted as treatment emergent and attributed to the last treatment taken. Events that occur during the washout period between study periods will be counted as treatment emergent and attributed to the previous treatment taken. The time period for collecting AEs ("active collection period") for each participant begins from the time the participant provides informed consent.

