6.5.1. Adverse Events

Adverse events will be reported in accordance with the CaPS.

Participant discontinuations due to adverse events will be detailed by treatment. Data will be reported in accordance with the CaPS.

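### The TEAE tables set about 4 days on PF-07817883 alone beside 31 to 38 days on the combination, so crude counts favour PF-07817883 alone even with no interaction

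*SAP*

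**What the plan says.** SAP 6.5 defines three consecutive safety windows. PF-07817883 alone is "from Period 1 Day 1 up to just before the first dose of itraconazole administered alone in Period 2 Day 1". Itraconazole alone fills the time from there to the second PF-07817883 dose. The combination is "from coadministration of PF-07817883 with itraconazole in Period 2 Day 4 through the end of the study". Tables split by these three treatments are to be used to judge the risk of each.

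SAP 3.5.1 takes events up to 35 days after the last dose and has them "counted as treatment emergent and attributed to the last treatment taken". Protocol 6 states that "study intervention refers to PF-07817883 or itraconazole", so the last dose is itraconazole on Study Day 11. Protocol 8.4.1 collects AEs "through and including a minimum of 28 calendar days, except as indicated below, after the last administration of the study intervention".

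On observation, Protocol 4.1 says of participants that "they will be discharged from the PCRU on Period 2 Day 8 (Study Day 12) following completion of all assessments". After that: "A follow-up (which may be a phone call) will be made to participants approximately 28 to 35 days from administration of the final dose".

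On the form of the summary, SAP 5.2.1 gives numbers and percentages for categorical data, SAP 6.4.3 only lists exposure, and SAP 6.5.1 says "Adverse events will be reported in accordance with the CaPS". CaPS is not reproduced. The SAP text states no common window, no person-time denominator and no adjustment for time at risk.

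**The concern.** The first secondary objective is the safety of PF-07817883 with and without itraconazole. These descriptive tables are the natural place for a reader to look for that contrast. The two columns to be read against each other differ in two ways that have nothing to do with itraconazole:

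- **Time.** One column covers about four days and the other a month or more. Ordinary background events accumulate in the longer one.
- **Ascertainment.** The PF-07817883-alone window is spent wholly in the unit. The combination window is 4 days in the unit, then 27 to 34 days at home with one scheduled contact.

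With about 12 participants, one to three extra people with a background event can look like a tolerability signal for the combination. Scheduled laboratory, vital-sign and ECG summaries do not appear to be affected, since they rest on fixed assessment times.

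**Working it through.** **Inputs from the documents.** First itraconazole dose about 1 h after the 96 h sample (Protocol 4.1); PF-07817883 doses on Study Days 1 and 8; last itraconazole dose on Study Day 11; discharge on Study Day 12; follow-up 28 to 35 days after the final dose; about 12 participants.

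**Check against the plan's own figure.** The second PF-07817883 dose falls (8 − 1) × 24 = 168 h = 7.0 days after the first, which reproduces the 7-day interval in Protocol 4.1.

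**Window lengths.**

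- PF-07817883 alone: 96 + 1 = 97 h = 4.04 days.
- Itraconazole alone: 168 − 97 = 71 h = 2.96 days.
- Combination: (11 − 8) + 28 = 31 days, or (11 − 8) + 35 = 38 days. Of this, 12 − 8 = 4 days are in confinement and 27 or 34 days follow discharge (27/31 = 87%, 34/38 = 89%).
- Ratio of the combination to PF-07817883 alone: 31/4.04 = 7.7; 38/4.04 = 9.4.

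Protocol 4.4 ties the end of the study to the last participant in the trial; the 38-day limit for an individual comes from the 35-day lag in SAP 3.5.1.

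**Expected counts with no drug effect.** Two quantities are assumed because the documents give neither: a constant background rate r per participant-day, and the fraction c of post-discharge AEs that is captured. Effective days in the combination window are 4 + 27c or 4 + 34c. The expected number of participants with at least one AE is 12 × (1 − exp(−r × effective days)).

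At r = 0.01, PF-07817883 alone gives 12 × (1 − exp(−0.0404)) = 0.48. The combination gives:

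| Capture c | Effective days | Expected participants |
|---|---|---|
| 100% | 31 to 38 | 3.20 to 3.79 |
| 50% | 17.5 to 21 | 1.93 to 2.27 |
| 25% | 10.75 to 12.5 | 1.22 to 1.41 |
| 10% | 6.7 to 7.4 | 0.78 to 0.86 |

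At r = 0.005 the contrast is 0.24 against 0.40 (10%, 27 days) to 2.08 (100%, 34 days). At r = 0.02 it is 0.93 against 1.50 to 6.39. Over the whole grid the range is 0.2-0.9 for PF-07817883 alone and 0.4-6.4 for the combination.

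**Where the direction would turn.** Event counts are equal when 4 + 27c (or 4 + 34c) = 4.04, that is, c of about 0.1% to 0.2%. If only 10 of 12 participants enter the combination window, the equation is 4 + 27c (or 4 + 34c) = 4.04 × 12/10, and c is about 2.5% to 3.1%.

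**A matched window.** From 0 to 96 h after each dose, 12 × (1 − exp(−0.04)) = 0.47 in both periods.

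**Per-day rates over the full window do not repair it.** The apparent rate divided by the true rate is effective days over total days. With c = 25% it is 10.75/31 = 0.35 or 12.5/38 = 0.33; with c = 10% it is 6.7/31 = 0.22 or 7.4/38 = 0.19. The bias then runs the other way and hides events on the combination.

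**The case against.** The best case for the plan has five parts.

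- **Nothing is compared formally.** No hypothesis is tested, no AE difference or ratio is specified, and SAP 6.5 discloses where each window starts and ends. This is true and limits the consequence. But the objective is framed as with and without itraconazole, and the tables put the columns side by side.
- **CaPS may already supply a matched or exposure-adjusted table.** This cannot be excluded. What can be said is that the SAP text fixes unequal windows and names no such table. If CaPS has one, a sentence in SAP 6.5 closes the point.
- **The size is assumed.** This stands. Background rate and capture are not in the documents, and the combination range of 0.4 to 6.4 participants is wide. At 10% capture and 0.01 per day the gap is under half a participant. If capture were nil, or every AE fell within four days of dosing, the ratio of counts would be 4.0/4.04 = 0.99. A first-dose or confinement effect in Period 1 could also offset it. However, clustering after dosing that is common to both periods does not remove background events from the longer window. AEs are also actively elicited at follow-up, so capture should not be nil.
- **Attrition.** With 10 participants in the combination window, 10 × (1 − exp(−0.067)) to 10 × (1 − exp(−0.074)) gives 0.65 to 0.71 instead of 0.78 to 0.86 at 10% capture. Counts fall somewhat; percentages barely change.
- **Causality and intensity are assessed for each AE** (Protocol Appendix 3). This helps in reading a late event but does not equalise the columns.

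A matched window would also leave itraconazole's own AEs on Study Days 8 to 11 and any period effect in the Period 2 figure. Those are limits of a fixed-sequence design. They do not justify adding an avoidable imbalance in time and ascertainment.

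**Conclusion.** The concern holds. The window lengths and the 7.7- to 9.4-fold ratio follow from the documents without assumption, as does the assignment of all follow-up events to the combination. Higher crude counts for the combination with no interaction follow if some background AEs occur after discharge and more than a few percent of them are captured. How much higher cannot be fixed from the documents: under a constant rate of 0.01 per participant-day it is 0.5 participants against anything from 0.8 to 3.8. The effect is confined to descriptive TEAE summaries for a secondary objective. The change is worth making because it is cheap.

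**What to change.** In SAP 6.5:

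1. Add a TEAE summary restricted to onset from each PF-07817883 dose to 96 h after it (Period 1 Day 1 and Period 2 Day 4). Both intervals lie wholly in confinement. Name this table as the one for the descriptive reading with and without itraconazole.
2. Show events with onset after Period 2 Day 8 in a separate follow-up column.
3. Keep the three-treatment table as the overall safety record, and print the length of each window in its column header.
4. State with the matched table that Period 2 still includes itraconazole's own AEs and any period effect.

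The cost is a few lines of SAP text and one table from data already collected. The downside is small: late-onset events, including those while itraconazole is still being eliminated (last dose Study Day 11, effective half-life stated as 24 h in Protocol 4.2), fall outside the matched table. They remain in the follow-up column and the overall table.
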